Hypothesis 1: CV vs. WT will exhibit higher cortico-striatal and striato-limbic and intrastriatal RSFC (Figure 1B and C: Base) and report higher craving for MA at baseline.

SA 2: Determine the effect of *acute* oral MA or placebo (PBO) administration on the interaction of *htaar1* CV vs. WT genotype on RSFC, craving, cognitive control, attention and subjective experience in MUD.

Hypothesis 2: Acute MA administration will lower RSFC in both genotypes, with a blunted decrease in the CV group (Figure 1C: MA and PBO).

Hypothesis 3: The CV group will exhibit, compared to WT, blunted effect of MA administration on craving, subjective experience and tests of attention and cognitive control.

Experimental Design:

Recruitment: MUD and control subjects will be recruited by advertisement from VAPORHCS, OHSU, community assistance programs. Advertisements will also be posted online externally utilizing Craigslist, the VAPORHCS web page, the quarterly newsletter (Veteran Connection), the VA Facebook page OHSU's Research Opportunities pages, the OHSU website (MARC page or dedicated lab page), Indeed.com, Ziprecruiter, Google Jobs, Localwise.com, Skoll.org, and community news publications (Street Roots, Portland Mercury, Willamette Weekly and possibly others). Approved flyers will be distributed throughout the community (retail locations, community assistance programs, primary care clinics, emergency departments, dental clinics, community outreach programs). All Craigslist ads, other job boards and social media will have email reply turned off so that potential participants will have to call the study team. Facebook posts will have a link to a PDF of the approved flyer, which will direct any subjects to contact the study team. All content published for both internal and external promotion will utilize the approved flyer or other approved language so that anyone interested in the study will have to call the study team for more information. Newspaper, job board and social media ads will utilize the approved Craigslist ad language unless other language is specifically approved. If potential subjects are referred by their VA providers, the provider will first ask permission from the subject to discuss the research project. If the subject gives permission, the provider will document this either in a CPRS note or encrypted email to the study team. VA providers may also send out our approved flyer with their regular occurring mail outs to their clients.

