Research Match and OHSU OCTRI Research Volunteer Registry will be used to recruit potential subjects. An IRB approved description of the study will be sent to individuals by Research Match who meet criteria for the study. If the individual indicates they are interested, their contact information (i.e. name, mailing address, email, phone number) will be sent through Research Match to the [name] Lab Research Match account. This information will remain in the ResearchMatch system and/or be exported to the OHSU RDS server. OHSU OCTRI Research Volunteer Registry will provide contact information of individuals who meet study criteria and this information with be stored on the OHSU RDS server. Research assistants will contact these individuals using phone or email to set-up a phone screen. Subjects will be emailed via [contact] to set up a phone screen. The [name] lab has substantial capacity and expertise to recruit MUD participants. Per NIDA guidelines, MUD subjects who have been referred to appropriate VA or community treatment facilities but will not be in drug treatment (court-mandated or otherwise) when recruited or while participating in the study (if subjects choose to join a treatment program during their participation in the study they will be withdrawn from the study and will not be administered methamphetamine). The community assistance programs we work with interact with precontemplative methamphetamine users regularly. Subjects may also be recruited by calling participants who previously consented to being contacted for future research after enrollment into the MARC study (eIRB 8702). As the IRB previously approved, these subjects will be pulled directly from the MARC study, not from a contact information repository. CPRS will not be accessed for screening purposes. Subjects who call in response to advertisements are screened with a telephone script to verify likelihood of meeting criteria and, if indicated, given an initial appointment. Additional questions will be asked to screen for recent exposure and symptoms of COVID-19. If recent exposure or symptoms are disclosed, and the subject otherwise qualifies, we will wait to schedule them until they have self-isolated for two weeks from time of exposure and/or when their symptoms have completely resolved. Our screening criteria already excludes those who are at increased risk of severe illness from COVID-19; however some subjects who *might* be at an increased risk may still qualify to participate during modified operations including smokers and those with wellcontrolled moderate-to-severe asthma, hypertension, and/or high blood pressure. These subjects will be informed that they may be at higher risk for COVID-19 infection and they may not want to put themselves at risk by participating in research. A VA waiver of informed consent and authorization for screening/recruitment purposes will be requested to collect subject names, phone numbers, and email before potential subjects give formal informed consent. Email addresses will be collected on the screening form for scheduling purposes and, if the potential subject agrees, email will be collected to send an appointment confirmation email (Azure). Each subject will provide written informed consent before any data collection or additional screening takes place. Up

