* Subjects should have been using at least 100mg of methamphetamine (not prescribed), 5 days per week for at least one year

* Abstinent from methamphetamine for 48 hours on days of scans

CS groups:

• At least one exposure to a stimulant, either recreational or prescribed

Criteria for Exclusion:

All groups:

- * Allergies to stimulants or hypersensitivity to taking a stimulant in the past
- * Diagnosis of a psychotic or mood disorders (past diagnoses of depression allowed) (DSM-V)
- * Self-reported claustrophobia
- * Women who are pregnant or breast-feeding

* Positive urine drug screen result at any point during the study (except for amphetamines except for verified medical reason)

* Intoxicated on study days (see Abstention from Methamphetamine below)

* Clinically significant neurological, cardiovascular, endocrine, renal, hepatic or systemic disease that could compromise safe participation or confound outcomes (including hepatitis C, HIV, severe anemia, or liver disease)

* History of glaucoma

- * Metal in the body which is contraindicated for MRI or would compromise image quality
- * Current prescription use of stimulants, anti-psychotic drugs or anti-Parkinson's drugs
- * Use of monoamine oxidase inhibitors within 14 days
- * Use of serotonin reuptake inhibiters, serotonin norepinephrine reuptake inhibiters, triptans, tricyclic

antidepressants, Fentanyl, lithium, tramadol, tryptophan, bispurone, St. John's Wort, insulin, phenothiazines, guanethidine, acidifying/alkalinizing agents, CYP2D6 inhibitors, proton pump inhibitors

MUD Groups:

- Positive urine drug screen at any point during the study (except for meth or marijuana)
- History of any severe substance use disorders within the last 5 years, except for methamphetamine use disorder or tobacco use disorder

CS Groups:

- History of any severe substance use disorders within the last 5 years except tobacco use disorder
- Positive urine drug screen at any point in the study (except for marijuana or verified medical reason)

Enrollment: We will enroll up to 200 individuals into Part 1. Individuals will then be screened into Part 2 based on their genotype and if they have no contraindications for methamphetamine administration or MRI. Subjects must have the WT Group or CV Group to screen into Part 2 and we will continue to enroll subjects into Part 2 until we have 18 completers in each of the 4 WT and CV groups.

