Risks of MRI: Subjects who are claustrophobic may become frightened in the MRI machine. Subjects with metal fragments, wire sutures, staples, implanted pacemakers or defibrillators or metal fragments from welding or shrapnel from combat are at risk from damage due to movement or heating of metal fragments in the 3T magnetic field. Participants will be systematically assessed for ferromagnetic metallic foreign bodies and excluded if there is any doubt. Rarely, subjects experience vertigo, a metallic taste or muscle stimulation. Although none are currently known, there may be unknown risks to fetuses in from the MRI procedure and so pregnant women are excluded.

Risks of Methamphetamine Administration: MA has a high potential for abuse and dependence with continual use. Hypersensitivity reactions are known and include angioedema and anaphylactic reactions. Sudden death, stroke, and heart attack have been reported with use of high doses of methamphetamine and other stimulants. According to FDA-approved Desoxyn® labeling, adverse events include: elevation of blood pressure, tachycardia and palpitation, psychotic episodes, dizziness, dysphoria, overstimulation, euphoria, insomnia, tremor, restlessness, headache, exacerbation of motor and phonic tics and Tourette's syndrome, diarrhea, constipation, dry mouth, unpleasant taste, gastrointestinal disturbances, urticarial, impotence and changes in libido, frequent or prolonged erections, rhabdomyolysis, suppression of growth in children, and alopecia. Stimulants can cause teratogenic and embryocidal effects during pregnancy and amphetamines can be excreted in human milk. Our subjects typically self-administer much higher doses of MA than are used in this study.

NIDA guidelines for administering abusable substances to individuals currently addicted to drugs:

1) A serious and concerted effort be made to link these individuals to drug abuse treatment. We will engage participants (all of whom will be current MA users and meet criteria for MUD) in education about MA addiction and we will offer referral to VA or community treatment at each visit.

2) Inclusion of medical examination and screening to assure the absence of any medical or mental condition for which further drug exposure would be contraindicated. This examination will be performed at the initial visit and subjects will be excluded for co-morbid medical or psychiatric conditions that contraindicate low doses of MA.

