3) A thorough assessment of the risks entailed if participants are to be exposed to higher doses, rate of

administration, and/or new route of administration than they would normally encounter by their own choice in their usual circumstance. Subjects recruited for this study typically self-administer up to 500 mg MA orally, intravenously, by smoking or insufflation. The low oral dose of MA used in this study is considerably less than subjects routinely self-administer.

Risks to Confidentiality: There are risks to confidentiality, particularly sensitive information about genetics, medical history and drug use. Breaches in confidentiality may result in loss of privacy and could result in monetary loss due to identity theft. It could also carry other risks, such as embarrassment or affect current or future job status, relations with your family, immigration status, parental right or responsibilities or status in the community. Banking specimens and data in a biorepository and sharing data with the University of Minnesota slightly increases the risk of a breach of confidentiality.

Risks of X-Ray: If there is a chance that subjects have metal fragments lodged in their eyes or face, we will perform an orbital x-ray to check. Risks include exposure to radiation of about 40 mrems. No increased risk has been scientifically demonstrated from this level of exposure, though a very small increase in cancer risk may exist.

Risks of Specimen Collection: Blood drawing may cause pain or bruising at the site and carries a small risk of infection. There is also a risk of fainting during or after a blood draw.

Adequacy of Protection against Risks

A clinician will be available to consult with any participants who experience discomfort for any reason during the study visit. Subjects will be asked to remain in laboratory either until the problem has been resolved or immediate referral to appropriate treatment is accomplished. Subjects not in need of emergent treatment will be offered referral to counseling or other support resources as appropriate. The subject may request termination of the assessments at any time. Subjects may refuse any single non-critical procedure in the study if it makes them uncomfortable without disqualification from the rest of the study.

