Protection of Risks of Questionnaires, Computer Tasks and Cognitive Testing: Subjects or study staff will terminate questioning or task performance at any time that the subject becomes upset or overly frustrated and does not wish to continue.

Protection of Risks of MRI: Subjects are interviewed extensively to screen for any contraindication to MRI, e.g., surgical aneurysm clips, pacemaker, prosthetic heart valve, neuro-stimulator, implanted pumps, cochlear implants, metal rods, plates or screws, previous surgery, hearing aids, history of welding, metal shrapnel or tattoos with ferro-magnetic particles. If there is any doubt, the subject will be excluded. The research team will obtain orbital x-rays if subjects have any history of welding, grinding or other exposure to metallic particles that could lodge in the eye. Pregnant women (negative urine pregnancy test required before the scan), because of the unknown risk to the fetus, will also be excluded. Participants will be taken to a mock MRI prior to the procedure if they are concerned about claustrophobia. If a subject becomes frightened during the procedure it can be terminated immediately.

Protection of Risks of Methamphetamine Administration: The study team will thoroughly screen potential participants for medications and conditions which would contraindicate use of stimulants. This will include a medical history, family medical history and a brief physical performed by a study physician. Women will be screened for pregnancy at the beginning of each visit and will be removed from the study if found to be pregnant. After the administration of MA, subjects will be continuously monitored for blood pressure and heart rate changes by research staff and during the MRI. Participants will complete a safety questionnaire before they can leave the lab after MA administration and will not be allowed to drive on study visits where MA may be administered.

Protection of Risks to Confidentiality: Study data will be coded and kept separately from any HIPAA Identifiers. Paperwork will be kept in locked cabinets in a locked office at the Portland VA. Digital data, including the spreadsheet linking the subject ID to personally identifiable information, will be kept behind password protected applications and spreadsheets. Data and specimens in the biorepository will not be linked to any personally identifiable data and the code linking spreadsheet will be encrypted once the original study is completed.

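### Controls are given 15–30 mg methamphetamine, yet a person whose severe methamphetamine use disorder ended more than 5 years ago meets every listed control criterion

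*Combined protocol and SAP*

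**What the plan says.** The recruitment text plans 72 completers in four groups of 18. Two of these groups are called healthy controls, a term the protocol does not define. MA Administration and Randomization gives every Part 2 subject MA at one visit and placebo at the other, with MA doses of 15, 20, 25 or 30 mg by body weight and no exception for controls. MA Metabolites confirms that controls receive study drug, since it schedules their samples after dosing at visits 3 and 4.

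Under Criteria for Exclusion, CS Groups, the diagnostic substance-use rule is "History of any severe substance use disorders within the last 5 years except tobacco use disorder". A second rule excludes a positive urine screen, apart from marijuana or a verified medical reason. To be included, a control needs one past stimulant exposure, which may be recreational; no upper limit is set. The psychiatric exclusion for all groups covers psychotic and mood disorders and does not mention substance use disorders.

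The dosing rationale is written about users. Risks of Methamphetamine Administration says "Our subjects typically self-administer much higher doses of MA than are used in this study". Point 3 of the NIDA guidelines says "Subjects recruited for this study typically self-administer up to 500 mg MA orally, intravenously, by smoking or insufflation". Point 1 describes the participants as people "all of whom will be current MA users and meet criteria for MUD".

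Protection of Risks of Methamphetamine Administration adds a general screen: "The study team will thoroughly screen potential participants for medications and conditions which would contraindicate use of stimulants".

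**The concern.** The exclusion is limited by severity and by time. Both limits leave room for people with a history of MUD to be given MA under a control label. The clearest case is someone in long remission from severe MUD. The protocol itself warns of MA's abuse and dependence potential with continued use, and says that participants are not expected to benefit individually. Re-exposing a person in remission is a different decision from dosing a current heavy user or a person with no such history, and the protocol gives no reasoning for it. What is at stake is mainly participant safety. A secondary effect is that the controls would be less cleanly separated from the MUD groups.

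**Working it through.** No power or sample-size figure is involved. The check sets the written rules against four kinds of candidate, then asks whether the safety rationale covers controls.

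**1. Who passes the listed control criteria**

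| Candidate | Result under the listed rules |
|---|---|
| Severe MUD that ended more than 5 years ago, urine negative | Not excluded |
| Current or past mild or moderate stimulant use disorder, urine negative at each screen | Not expressly excluded |
| Severe MUD within the last 5 years | Excluded by the diagnostic rule |
| MA-positive urine with no verified medical reason | Excluded by the control urine rule |

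The all-groups urine rule makes an exception for amphetamines, but the control rule is stricter and decides the last row. Urine testing cannot detect a remitted disorder, so it does nothing in the first row.

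**2. Whether a general clause closes the first row**

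Three clauses could. Enrollment admits to Part 2 only people without contraindications to MA. Point 2 of the NIDA guidelines excludes medical or psychiatric conditions that contraindicate low-dose MA. The protection section screens for conditions that contraindicate stimulants. All three depend on clinical judgement, and none names use-disorder history. Beside a written rule that stops at severe disorders within 5 years, a screener could reasonably take older or milder disorders as acceptable.

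**3. Whether the dose rationale covers controls**

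- MUD participants must have used at least 100 mg of MA on 5 days a week. The top study dose is 30/100 = 30% of that amount, and 30/500 = 6% of the 500 mg that the protocol cites as an upper figure.
- Controls have no minimum beyond one stimulant exposure, so neither ratio applies to them.
- Controls number 2 × 18 = 36 of 72, or 50% of planned completers. The statement that all participants are current users with MUD cannot hold for that half.

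**4. What the team did before**

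In PS4, the pilot in which 12 healthy controls took oral MA, none met criteria for any substance use disorder; whether this meant current or lifetime is not stated. PS1 defined its controls by the absence of lifetime dependence, apart from nicotine and caffeine. The present rule is looser than PS1's lifetime standard and does not carry over PS4's absence of any disorder. No reason is given.

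**The case against.** The strongest reply is that people with current MUD will not in practice be enrolled as controls. The protocol contrasts healthy controls with MUD individuals, assesses entry partly by psychiatric diagnosis, tests urine at screening and on scan days, and lets clinicians refuse contraindicated candidates. Most of this stands. A reader might infer from the criteria that active methamphetamine users will be dosed as controls; the documents do not support that. They show only that current mild or moderate disorder is not expressly barred.

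A reader might also combine two recruitment sentences, "MUD and control subjects will be recruited by advertisement from VAPORHCS, OHSU, community assistance programs" and "The community assistance programs we work with interact with precontemplative methamphetamine users regularly", and conclude that people in remission will be common among control candidates. The second sentence concerns current users, whom urine screens target. It is not evidence about people years past their disorder.

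Nor are controls unprotected. Medical screening, blood pressure and heart rate monitoring, the safety questionnaire before leaving, the driving restriction and access to a clinician apply to them too. The treatment-referral promise sits under guidelines for people currently addicted, so its absence for someone in long remission is not itself a defect. PS1 and PS4 are precedents, not binding standards; PS1 involved no MA dosing.

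None of this reaches the first row of the table. Severe MUD that ended more than 5 years ago is outside the diagnostic rule, invisible to urine testing and unnamed in the discretionary clauses.

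**Conclusion.** The concern holds for remitted severe MUD: the written criteria admit such a person as a control and schedule one MA dose of 15 to 30 mg. It holds more weakly for mild or moderate stimulant use disorder, where the criteria are silent but other features make enrolment less likely. The self-administration rationale and the description of all participants as current users do not apply to controls.

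The 36 controls are a ceiling on the number affected, not an estimate. The documents give no rate, so the true number could be anywhere from 0 to 36. The conclusion assumes that screeners apply the listed criteria as written and that the healthy-control label has no further definition elsewhere.

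A reader might go further and ask for controls to be free of every current substance use disorder. The documents do not support that on these grounds: the problem is exposure to MA, and the protocol deliberately tolerates marijuana-positive urine in controls.

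**What to change.** Keep both existing control exclusions. Add one line for the CS groups: *any lifetime stimulant use disorder (methamphetamine, amphetamine or cocaine) of any severity*. Ask about it in the existing telephone script and confirm it at the visit 1 eligibility review. Past stimulant exposure without a disorder would still qualify.

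In Risks of Methamphetamine Administration and in points 1 and 3 of the NIDA guidelines, limit the self-administration statements and the statement that all participants are current users to MUD participants.

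The cost is one exclusion line, one telephone question and a few wording edits. Staff must already identify, grade and date past disorders to apply the present rule, so no new procedure is needed. Some more controls will fail screening, probably few, but the documents do not allow a number; asking by telephone keeps most of these failures ahead of consent. Dosing, endpoints and sample size are unchanged.

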
to 100 current users of methamphetamine (MA) who meet DSM-V criteria for MA use disorder (MUD) and 100 controls will be recruited for this project and 36 from each group will complete all study procedures (we anticipate many will screen out based on their genetic screening for TAAR1). These 72 will break down into 4 groups of 18:

- MUD Wild Type (WT) Group: MUD individuals who are WT for the TAAR1 gene
- MUD Common Variant (CV) Group: MUD individuals who are hetero- or homozygous for the V288V SNP on the TAAR1 gene
- CS WT Group: Healthy controls who are WT for the TAAR1 gene
- CS CV Group: Healthy controls who are hetero- or homozygous for the V288V SNP of the TAAR1 gene

Data (including MRI scans) and specimens (saliva) may be pulled from the MARC Biorepository (mIRB 3164) to supplement subjects enrolled into this study for data analysis. Data and specimens will be coded and will not include any identifiers. A Waiver of Process of Informed Consent/Authorization will be obtained for analysis of these data/specimens and a DUA will be fully executed before data/specimens are removed from the repository. Repository data shared with this project may be sent to the University of Minnesota for analysis as described below in **Specific Outcome Measures and Hypotheses**. This data will be a Limited Data Set that includes imaging data (defaced), demographics such as age (no one over age 89), sex, treatment assignment (meth and placebo), TAAR1 genotype, substance use variables and survey scores. Data will be shared with study team members currently approved by the VA/OHSU joint IRB for this protocol. As this data is being shared from the repository (Sender) to Minnesota under this protocol (Recipient), a DUA between the repository and University of Minnesota will be fully executed before data is removed.

Inclusion/ Exclusion criteria: Entry criteria will be assessed based on self-report questionnaires, medical history and psychiatric diagnosis. Data/specimens pulled from the MARC biorepository will have come from subjects with very similar relevant inclusion/exclusion criteria which will be evaluated before inclusion.

Criteria for Inclusion:

All groups:

- * 18 to 55 years old
- * Homozygous or heterozygous for the hTAAR1 V288V genotype or wild type for hTAAR1 (Part 2)

MUD groups:

- * Subjects must have a positive urine drug screen for methamphetamine during visit one
- * Meets current criteria for methamphetamine use disorder

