Abstention from Methamphetamine: MUD subjects will be asked to abstain from using methamphetamine on the day of Visit 1 and 2 will be asked to abstain from using methamphetamine for 24 hours prior to Visits 3 and 4. If subjects come to their appointments intoxicated, they may be dropped from the study or rescheduled. **Subject selection and randomization:** [name] laboratory at the Portland VA will genotype the *htaar1* in Part 1 participants to identify all V288V variants (members of the [name] lab may also prep samples but will not read results). The CV Groups will be composed of subjects who are heterozygous or homozygous for the CV SNP without any other variant, while the WT Groups will include those who have the wild type genotype. The *htaar1* gene will also be sequenced in its entirety (the [name] lab will purify the DNA and then send it to the OHSU Core lab) so that individuals with rare non-synonymous *taar1* can be identified *post hoc* and analyzed separately. We will screen subjects until we have 18 subjects in each of the four CV Groups and the WT Groups balanced by age and sex (a research assistant not involved in the subject evaluations will check the balance and will adjust accordingly). As the population gene frequency is 23%, we expect to

Visit Number	1	2	3	4
	Part 1		Part 2	
Informed Consent	\checkmark			
Review Study Eligibility	✓			
Medical History	✓			
Family History	✓			
Neuropsych Assessment		✓		
Computer Tasks		✓		
Vital Signs	✓		✓	✓
Urine Drug Screen/Pregnancy		1		
Test	v	•	v	v
Cheek Swabs	✓			
EKG	✓			
Study Drug or Placebo				
Administered			v	v
MRI Scans			✓	✓
Blood Draw	✓		✓	✓
Saliva Collection	✓		✓	✓
Questionnaires		✓	✓	✓
Total Time (hours)	3	3	8	8

genotype up to 200 individuals to ensure two groups of age and gender matched subjects. We will replace dropouts until we have 18 completers in each group (for a total of 72 completers). The study team will be blind to genotype. The [name] lab will determine genotype and refer subjects back to the study team for inclusion in blocks of six subjects (three CV and three WT). If more than three CV or WT subjects are genotyped before three of the other group, then participants will wait for enrollment into Part 2 until the current block of six subjects is complete. Genotype data will be provided to the pharmacy to allow stratification by genotype during randomization.

Visit Schedule

Part 1: Visits 1 and 2: Consent/Screening: Subjects will be consented and then screened for

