Part 2: Visits 3 and 4: Scan Days: All study procedures will happen at the Portland VA except for the MRI scans which will take place at the OHSU AIRC. MA administration and questionnaires may take place at either the VA or OHSU. Subjects are asked to abstain from MA for 72 h before the scan. A urinalysis will be performed to ensure that women are not pregnant and that no other drugs are present. Subjects will undergo a baseline MRI scan approximately 1 hour after the start of each visit followed by drug administration (placebo or MA) and a second scan 1.5 hours after that. Blood samples (3 mL) and/or oral fluid samples will be drawn before drug administration and after the second scan to quantify MA levels. At the Portland VA, during visit 2, up to 15 mL blood will be drawn and a cheek swab will be taken and both will be stored in the MARC biorepository located at the Portland VA. Blood may be stored as plasma or whole blood. Surveys and neurocognitive assessments will be performed before and after each scan at the Portland VA. Pulse, respiration, and pulse oximetry will be monitored throughout each scan. Each visit will last approximately 8 hours, and the subjects will be monitored (blood pressure, heart rate) closely throughout. The Systematic Assessment for Treatment Emergent Effects (SAFTEE) will be used to screen for adverse effects at the end of the day and the individual will be provided with discharge instructions in both verbal and paper form, which informs the subjects that these medications have the potential to impair driving and operation of heavy equipment. Subjects will be given a list of drugs that should be avoided for their interactive potential with MA and will be provided with a phone number to call [name] with questions. A break of at least two days will be required between visits to allow washout. Subjects will be required to take public transit or have a designated driver for each visit. Subjects may be offered a meal from OCTRI nutrition services, snacks or gift card to the VA canteen during each of these visits. Subjects may be asked to be a backup subject for Visits 3 or 4. Double-booking will help ensure the best use of time and resources. If both participants show up for the visit and we do not complete your visit, they will be paid \$50 in prepaid debit cards for your time.

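### Three different methamphetamine abstinence intervals (24, 48 and 72 h) are set for the same MUD scan visits, and the 24 h request conflicts with the 48 h inclusion criterion

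*Combined protocol and SAP*

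**What the plan says.** Three places in the protocol set a methamphetamine (MA) abstinence interval for MUD participants at Visits 3 and 4, which are the scan days.

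- Criteria for Inclusion, MUD groups: "Abstinent from methamphetamine for 48 hours on days of scans".
- Abstention from Methamphetamine: MUD participants "will be asked to abstain from using methamphetamine for 24 hours prior to Visits 3 and 4".
- Part 2: Visits 3 and 4: Scan Days: "Subjects are asked to abstain from MA for 72 h before the scan".

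All three are current text, and nothing says which governs. The exclusion item on intoxication sends the reader to the Abstention section, where the 24 h figure stands.

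On timing, the scan-day section adds: "Subjects will undergo a baseline MRI scan approximately 1 hour after the start of each visit". The study dose follows that scan.

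On enforcement, the Abstention section says: "If subjects come to their appointments intoxicated, they may be dropped from the study or rescheduled". The inclusion and exclusion section says: "Entry criteria will be assessed based on self-report questionnaires, medical history and psychiatric diagnosis". On scan days, "A urinalysis will be performed to ensure that women are not pregnant and that no other drugs are present". The MUD exclusion criteria exempt a methamphetamine-positive urine screen. Under MA Metabolites, MUD participants give two samples for MA quantification at each scan visit, and the scan-day section places the first before dosing. The samples are frozen and then sent to an outside laboratory.

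**The concern.** Time since last use matters enough to the investigators that they made it an eligibility criterion. Yet the section devoted to abstention asks for half the required interval. Staff who follow that section, or participants who do as it asks, can breach the inclusion criterion without departing from the instruction they were given.

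A shortfall is plausible in this population. MUD entrants are expected to have been using on 5 days a week for at least a year and are not in treatment. That leaves about 7 − 5 = 2 non-use days in a week, so reaching 48 or 72 h depends on a clear instruction.

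The measurements at stake are baseline resting-state connectivity and craving, on which Hypothesis 1 compares the genotype groups. If the longer interval is not applied, time since last use at that baseline becomes less controlled than the eligibility criterion intends.

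**Working it through.** The plan gives no calculation to reproduce. The check is whether the three intervals can be reconciled once their different reference points are allowed for.

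**Inputs**

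- Request in the Abstention section: 24 h before the visit.
- Inclusion criterion: 48 h on scan days, with no statement of whether this runs to visit start or to the scan.
- Request in the scan-day section: 72 h before the scan.
- Visit start to baseline scan: about 1 h (scan-day section).
- Visit length: about 8 h (scan-day section).
- Minimum break between Visits 3 and 4: two days (scan-day section).

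**Step 1. A participant who follows the 24 h request exactly**

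- Time since last use at the baseline scan: 24 + 1 = 25 h.
- Shortfall against the criterion, counted to visit start: 48 − 24 = 24 h.
- Shortfall against the criterion, counted to the baseline scan: 48 − 25 = 23 h.
- Shortfall against the 72 h request: 72 − 25 = 47 h.
- Time since last use at the very end of the visit: 24 + 8 = 32 h, still below 48 h.

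The choice of reference point therefore does not reconcile 24 h with 48 h.

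**Step 2. Can any pair coexist?**

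- 48 h and 72 h: yes. Asking for 72 h and accepting 48 h is coherent, and anyone who honours 72 h meets all three figures.
- 24 h and 72 h: no. They are two different requests to the same people for the same visits.
- 24 h and 48 h: no. The request is shorter than the criterion.

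**Step 3. What would catch a shortfall on the day?**

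- No scan-day item on time of last use is described.
- A methamphetamine-positive urine screen does not exclude a MUD participant, and the scan-day urinalysis is described as a check for pregnancy and other drugs.
- The pre-dose samples are frozen and assayed off site, so no result is described as available before scanning.
- The one action stated in the Abstention section concerns participants who arrive intoxicated.

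**Step 4. Would 72 h fit the visit schedule?**

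The Visit 3 study dose comes after that visit's baseline scan, so it is given more than about 1 h into the visit and less than 8 − 1 = 7 h before its end. If the two-day break is read as 2 × 24 = 48 h from the end of Visit 3, the time from that dose to the Visit 4 baseline scan is at most about 7 + 48 + 1 = 56 h. This is under 72 h. A participant given MA at Visit 3 could therefore miss a 72 h rule through the study's own dose.

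**The case against.** The strongest reply is that the 48 h figure is an inclusion criterion tied to scan days. A participant at 25 h does not qualify that day, whatever the Abstention section asks. This stands in part. A reader might infer that the current text lets time since last use range from about 25 h upward, and the documents do not support that. If the criterion is applied, the floor is 48 h. If it is not, 24 h is only a request, so 25 h is not a floor either. The 25 h figure describes one scenario: the shorter request is honoured exactly and the criterion is not enforced. What remains missing is the operational step for a sober participant who is short of 48 h.

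The pre-dose MA assay is also a real mitigation. It cannot decide whether to scan, but it gives an objective measure of residual MA that could be examined afterwards, although no such analysis is stated. Last use might also be asked on a form that the protocol does not reproduce.

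A reader might further infer that the urine screen could not reveal recent use. The documents show only that a positive methamphetamine result does not exclude and that the scan-day test is described for other purposes. They give no detection window.

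Finally, the sponsor could argue that 24 h is the intended figure and that the criterion should be amended instead. The documents do not settle intent. However, two of the three statements call for at least 48 h, and one of those is an eligibility criterion.

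**Conclusion.** The inconsistency is certain and is not a matter of reading. The 48 h and 72 h figures are compatible. The 24 h figure is not, by about 23 h at the baseline scan or 24 h at visit start. The calculation assumes exact adherence to the 24 h request and the stated 1 h lag.

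The consequence is conditional. If staff follow the Abstention section and the criterion is not enforced, time since last use at the Hypothesis 1 baseline could be well under 48 h. How many visits this would touch cannot be estimated from the documents.

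A reader might conclude that the genotype comparison is biased, but that is not shown. Bias would need time since last use to differ between the variant and wild-type groups. The documents give no evidence that it would, and the study team is blind to genotype, which limits differential handling by staff. The point should be fixed because a stated rule conflicts with eligibility and the remedy is cheap.

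**What to change.** - Replace the 24 h figure in Abstention from Methamphetamine so that this section, the MUD inclusion criterion and the scan-day section all state one interval, counted back from the baseline scan. Keep 48 h as the minimum to match the criterion.
- If 72 h is intended, state that it refers to non-study MA, or lengthen the two-day minimum break between Visits 3 and 4. Otherwise the Visit 3 dose can fall inside the window.
- Record self-reported date and time of last use before the baseline scan at both visits.
- State, beside the sentence on intoxicated arrivals, that MUD participants who fall short are rescheduled.

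The cost is wording changes in three places, one extra recorded item and some more rescheduling. A longer break, if chosen, would also lengthen participation. The new item is self-report, so it documents time of last use without verifying it.
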